**Maintenance of Cohort.** Research staff will form on-going relationships and maintain contact with subjects. Our experience indicates this improves likelihood of participants' willingness to perform follow-up assessments. In addition: (1) At baseline, participants will be interviewed to determine whether they will be available for the entire study duration; (2) Participants will be excluded if unable to comply with birth control methods; (3) Participants will provide names and contact information of at least two relatives or friends and permission to contact them if they move without notifying investigators; (4) At each assessment, participants will be asked if they have plans to move; and (5) We requested funds in the budget to reimburse participants for completion of the assessments.

**Assessment Procedures.** Figure 2 below shows assessment schedule and measures. Major assessment at: baseline, during Stage 1 treatment (month 1, 2), post-Stage 1 treatment (month 3), during Stage 2 treatment (month 4, 5), post-Stage 2 treatment (month 6), and follow-ups at 6- and 12-months after completing Stage 2 treatment (i.e., 18 months after starting treatment). Outcomes assessments will be done by independent evaluators not involved in the treatment delivery and blind to treatment assignments.

**Assessment Training.** Independent assessors will receive training in diagnostic interviews from investigators following established protocols. Interviewers, once certified, will receive ongoing supervision to ensure consistent use and prevent drift. [name] will do inter-rater reliability studies, which he has published for BED ([name] et al., 2004) and psychiatry (Zanarini et al., 2000).

**Eligibility and Baseline Assessment.** Potential subjects will be assessed by clinicians who describe the treatment study and procedures, and obtain informed consent. Baseline assessment (two meetings) will include two interviews, the MINI (Sheehan et al., 2014) and EDE (Fairburn et al., 1993), to generate lifetime and current psychiatric diagnoses and detailed current eating disorder features and (BED) diagnoses.

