#### **Assessment of Treatment Outcome and Time Course.**

Primary Measures: (1) Binge-eating frequency (EDE); (2) weight (measured weight and height and BMI); for Stage 2 LDX vs Placebo test: "Relapse" to DSM-5 threshold of once-weekly binge eating on EDE

Secondary Measures: (1) "remission" (zero binges past 28 days on EDE; eating disorder pathology (EDE global), depression (BDI-II); for exploration of mediators: (2) eating behaviors (EDE, TFEQ, FCI-II), executive control and impulsivity (BIS-11, DDT, Trails) and selected metabolic measures (lipid profiles, HbA1c, blood pressure, HR) to characterize metabolic outcomes and allow comparison with RCTs for LDX and NB.

**Figure 2.** Grid depicting when each measurement is obtained

Assessment Points	BASELINE (2 MTG)	DURING RX STAGE 1 1-MONTH	DURING RX STAGE 1 2-MONTH	POST RX STAGE 1 3-MONTH	DURING RX STAGE 2 4-MONTH	DURING RX STAGE 2 5-MONTH	POST RX STAGE 2 6-MONTH	6 AND 12- MO FOLLOW- UP (18 MONTH TOTAL)
MINI Psychiatric Interview, Height, Credibility,	•							
EDE Interview, SF-12, GPAQ, Lipid Profile, HbA1C, Glucose	•			•			•	•
EDE-Q-I, BDI-II, GLTEQ, Weight, BP, HR	•	•	•	•	•	•	•	•
TFEQ-Restraint	•	•		•			•	•
DDT	•	•		•			•	
FCI-II, PFS	•	•		•	•		•	
BIS-11	•	•		•	•		•	•
ELOCS	•	•		•				
Trails, YFAS, BRS, Amphetamine Testing	•			•			•	
Placebo Ratings					•		•	
Start of New Treatments				•			•	•
Medical History Creatinine w/ EGFR PSQI	•			•				
Adverse Events		•	•	•	•	•	•	
Insulin	•			•				

Liver Function	•			•	• (Non- responde rs only)			
Pregnancy Test	•			•				

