- Delayed-Discounting Task (DDT), related to impulsivity, occurs when individuals choose smaller, more immediate rewards over larger rewards that would occur after a time delay (Green & Myerson, 2004). Analysis of responses with varied time delays and varied rewards indicates individuals' selections fall into a hyperbola-shaped pattern balancing delay and size of rewards (Green & Myerson, 2004) including obesity (Thomas et al., 2015). Individuals with BED show steeper responses than participants with obesity (Manwaring et al., 2011). Kirby is a DDT that asks participants to choose between two hypothetical rewards, one of which is after a delay. Amount of the short-term reward, long term reward, and time delay vary across 27 items, allowing for the computation of a "discounting rate" (i.e., when participants do not have a preference between smaller immediate reward and the larger but delayed reward) fitted to a hyperbolic discount curve (Kirby, 2009). These discounting rates have shown evidence of stability over 5-week ( $r=.77$ ) and 57-week ( $r=.63$ ) test-retest periods. DDT is relevant to neurobiologic models of BED (Balodis, [name], & Potenza, 2015) and models of LDX (Kessler et al., 2015).

- Short-Form-12 MOS Health Survey (SF-12); Ware & Sherbourne, 1992) taps health-related quality of life, with established reliability and validity (McHorney et al., 1993, 1994), and will be used to calculate quality-adjusted life years (**QALY**) per established methods (Revicki et al., 2005; Tsai et al., 2005) used in recent BED research on cost-effectiveness of LDX (Agh et al., 2016) and CBTgsh (Lynch et al., 2010; Dickerson, 2011).
- The Yale Food Addiction Scale 2.0 (YFAS 2.0 and YFAS-S 2.0) (Gearhardt et al., 2016) is a self-report questionnaire that adapted the 11 symptoms of substance dependence (as listed in the DSM-5) to assess addictive-type eating behaviors.
- Pittsburgh Sleep Quality Index (PSQI) is a widely used 19-item self-report measure which assesses sleep quality during the prior month (Buysse et al., 1989). The PSQI generates a global score ranging from 0 to 21; scores greater than five are indicative of poor sleep quality.
- Brief Resilience Scale is a psychometrically-sound brief measure assessing a person's ability to thrive and recover from stress.

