**(5) Secondary Aim:** Generate estimates of cost-effectiveness. We will compute within-study costs for CBT, LDX, CBT+LDX and SMART Stage 2 interventions. Repeated assessments will track additional clinician visits and medication use in our RCT as well as outside treatment contacts through the 18-months. SF-12, administered pre- and post-treatments and at follow-ups, will be used to calculate quality-adjusted life years (QALY) following established methods (Revicki et al., 2005) also used in BED studies of cost-effectiveness specifically of LDX (Agh et al., 2016) and CBTgsh (Lynch et al., 2010; Dickerson et al., 2011), as well as for obesity (Tsai et al., 2005; Malone et al., 2005) including obesity medications (Ara et al., 2012), and for similar SMART designs (switching medication for initial non-responders) in depression (Singh et al 2017). We will calculate incremental cost-effectiveness ratios (ICERs) for the various arms; in these ICERs, the numerator will be the incremental medical cost and the denominator will be the incremental effectiveness of the specific treatment compared to CBT. Confidence intervals for the ICERs will be determined using non-parametric bootstrapping. These ICERs will be compared to the two previous BED (Agh et al., 2016; Lynch et al., 2010) analyses and inform subsequent more definitive larger-scale effectiveness studies.

**POWER ANALYSIS:** We calculated our sample size to have at least 80% power at 2-tailed alpha level 0.025 (adjust for 2 outcomes) to detect clinically meaningful effects in Stage 1 for co-primary outcomes (binge eating and weight loss) and Stage 2 for primary outcome (relapse by initial Responders) at 2-tailed level of 0.05 according based on documented effects of the two treatment components (LDX and CBT). In Stage 1, with 180 subjects total (60 per treatment group), accounting for up to 20% dropout, we can detect medium effect sizes ( $d=0.64$ ,  $f=0.32$ ) for the between group comparisons with more than 80% power at two-sided alpha level of 0.025. These effect sizes are smaller than the effect sizes calculated based on data (Telch et al., 1990; [name] et al., 2005; McElroy et al., 2015, McElroy 2016) which ranged  $d=0.69$  to  $d=0.78$  for the comparison of CBT to LDX on binge-eating and was  $d=1.53$  for LDX vs CBT on percent weight loss. Dropout

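### The cost-effectiveness plan states no adjustment of incremental QALYs for baseline SF-12, although the trial collects it

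*Combined protocol and SAP*

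**What the plan says.** All references are to the combined protocol and SAP.

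- **QALY source.** Item (5) of DATA ANALYSIS states that SF-12, given before and after treatments and at follow-ups, "will be used to calculate quality-adjusted life years (QALY) following established methods". Supporting papers are cited. The SF-12 entry under Self-Report Questionnaires likewise says only that the instrument "will be used to calculate quality-adjusted life years". Neither place gives a utility mapping, a rule for combining visits, or a QALY horizon.
- **Estimator.** In the ICER, "the denominator will be the incremental effectiveness of the specific treatment compared to CBT".
- **Uncertainty.** "Confidence intervals for the ICERs will be determined using non-parametric bootstrapping". No regression, covariate or missing-data rule is attached to this analysis.
- **Horizon.** The nearest statement concerns resource use, where tracking covers "outside treatment contacts through the 18-months".
- **When SF-12 is measured.** In Figure 2 the row "EDE Interview, SF-12, GPAQ, Lipid Profile, HbA1C, Glucose" is marked at baseline, after Stage 1, after Stage 2 and at both follow-ups. The Assessment Procedures paragraph puts these at months 0, 3, 6, 12 and 18.
- **Stratification.** Randomization to Stage 1 Treatment stratifies on overvaluation of shape/weight and on BDI-II depression, not on SF-12.
- **General model.** The Overall Data Analysis Strategy lists time, treatment, their interaction and random subject effects. It names no baseline covariate, and item (5) does not send QALYs through that model.

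**The concern.** A QALY total contains the baseline utility and, because utilities are correlated within a person, also follows it at later visits. With 60 patients per arm, baseline SF-12 will differ somewhat between arms by chance. Randomisation makes the unadjusted difference unbiased over repeated trials. In the one trial that is run, though, part of the baseline difference stays in the ICER denominator. A non-parametric bootstrap of that difference describes its sampling error but leaves the realised imbalance in the point estimate and keeps the extra variance.

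At stake are precision and interpretability. The ICERs are a named aim, are to be set beside two earlier BED analyses, and are meant to inform larger studies. The plan also leaves room to choose between adjusted and unadjusted ICERs after the results are known.

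**Working it through.** **1. Is there a stated figure to reproduce?** No. The documents give no SD, correlation, standard error or power for SF-12 utilities, QALYs or ICERs.

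**2. Inputs.** From the documents: SF-12 at months 0, 3, 6, 12 and 18; 60 per arm, or 48 after 20% dropout (POWER ANALYSIS). Assumed here: QALY is the trapezoid area over 18 months; the utility variance is equal across visits and arms; the correlation rho between any two visits is exchangeable at 0.4 to 0.7. The SD cancels from the percentages.

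**3. Weights.** The trapezoid weights in months are 1.5, 3, 4.5, 6 and 3, which sum to 18. For time-averaged utility they are 1/12, 1/6, 1/4, 1/3 and 1/6. The sum of their squares is (1 + 4 + 9 + 16 + 4)/144 = 34/144 = 0.2361. Multiplying by 1.5 years turns average utility into QALYs and changes no ratio.

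**4. Formulas, in units of the utility variance.**
- V = variance of average utility = rho + (1 - rho) x 0.2361
- b = slope of average utility on baseline = 1/12 + (11/12) x rho
- R2 = b^2 / V
- Adjusted SE / unadjusted SE = sqrt(1 - R2)

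**5. Results.**

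| rho | V | b | R2 | Adjusted SE narrower by | Unadjusted SE wider by |
|---|---|---|---|---|---|
| 0.4 | 0.542 | 0.450 | 0.374 | 20.9% | 26.4% |
| 0.5 | 0.618 | 0.542 | 0.475 | 27.5% | 38.0% |
| 0.6 | 0.694 | 0.633 | 0.578 | 35.0% | 53.9% |
| 0.7 | 0.771 | 0.725 | 0.682 | 43.6% | 77.3% |

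The last two columns express the same gap from opposite ends. Simulation at 48 and 60 per arm agreed: about 26% wider at rho 0.4 and 74-79% wider at rho 0.7.

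**6. Carry-over.** The SD of a chance baseline difference is sqrt(2/60) = 0.18 utility SDs at 60 per arm, or sqrt(2/48) = 0.20 at 48. The expected share passing into average utility is b, 45% to 73%. At 60 per arm this shift has an SD of 0.450 x 0.1826 = 0.08 to 0.725 x 0.1826 = 0.13 utility SDs. Only 1/12 of the baseline difference enters mechanically; the rest comes through the assumed correlation.

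**7. Other assumptions.**

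| Scenario | Unadjusted SE wider by |
|---|---|
| 18 months, exchangeable 0.2-0.8 | 11-117% |
| 18 months, AR(1), 0.4-0.7 per 6 months | 16-46% |
| 6 months, exchangeable 0.4-0.7 | 39-96% |
| 18-month change from baseline against adjusted, exchangeable 0.4-0.7 | 14-38% |

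For the last row, the variance is V - 2b + 1. At rho 0.4 that is 0.542 - 0.900 + 1 = 0.642, against an adjusted variance of 0.542 x (1 - 0.374) = 0.339, and sqrt(0.642/0.339) = 1.38. Subtracting baseline reverses the carry-over instead of removing it: b - 1 runs from -0.55 to -0.275.

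**The case against.** **Silence is not a decision.** A reader might infer that the sponsor has chosen an unadjusted analysis. The text does not say so. It leaves QALY calculation to cited methods that cannot be consulted here, and those may adjust. This stands as a limit on the wording. It does not close the gap: the citations support how QALYs are calculated, while the between-arm estimator is described separately and without a covariate. The 2005 methods source cited first is also absent from the reference list.

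**The size is assumed.** Correct. SD, correlation, area rule and horizon are all outside the documents, and the AR(1) and change-from-baseline cases give smaller gains. The direction was the same in every case tried.

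**A reader might infer that chance imbalance could reverse the sign of the ICER.** The documents state no expected QALY difference, so there is nothing to compare the imbalance with. Nor do the percentages above describe the ICER, which is a ratio with cost uncertainty in its numerator.

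**A reader might compound 20% dropout at each stage to 0.8 x 0.8 = 64% complete, and call the analysis complete-case.** The documents support neither step. Stage 1 dropout is a ceiling. The figure of about 80 responders is 65-70% of all 120 medication patients (78 to 84), with no Stage 1 loss removed. CBT-only patients have no Stage 2 treatment. Patients are to be followed whether or not they finish treatment, and dropouts are invited back. A mixed model with categorical time could also yield a QALY as a weighted sum of visit means. What remains is narrower: a per-patient total needs every SF-12 visit, and item (5) says neither what happens when one is missing nor that the mixed model will be used.

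**Existing safeguards.** Baseline characteristics will be compared between groups, and stratifying on depression may limit SF-12 imbalance somewhat. Neither replaces adjustment.

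**The aim is exploratory.** It is a secondary aim to generate estimates, with no test or power calculation attached. This lowers the priority.

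**Conclusion.** The point holds as an unstated adjustment that would be a nearly free improvement. It is not an error in a primary analysis. Baseline SF-12 is collected and is not a stratifier, and the plan names no baseline term for incremental QALYs.

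Assuming an 18-month trapezoid area, equal variances and exchangeable correlation of 0.4-0.7, roughly 45-73% of a chance baseline difference would carry into the incremental QALY in expectation. It would not carry over in full. On the same assumptions the standard error of the QALY difference would fall by about 21-44% with adjustment. A reader might take that range as the excess width of the unadjusted standard error, but the matching excess is 26-77%. It is smaller under AR(1) or change-from-baseline QALYs. No claim about the sign of the ICER or the proportion with complete data is supported. Low priority.

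**What to change.** In item (5) of DATA ANALYSIS:

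1. State the utility mapping, the rule for combining visits into a QALY, and the QALY horizon.
2. Estimate incremental QALYs by regression on arm, baseline SF-12 utility and the two Stage 1 randomisation strata. Refit the regression within each bootstrap sample, so that the ICER interval uses the adjusted denominator.
3. State how missing SF-12 is handled: either multiple imputation within the bootstrap, or a mixed model adjusted for baseline with QALYs formed from the visit means by the same weights.

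Adjusting for a covariate measured before randomisation is valid in a randomised comparison, and fixing it in advance removes the choice between two ICERs at analysis. The cost is SAP wording and modest programming. No new data, visits or patients are needed.

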**STAGE 2 RCT – Secondary Aims:**

(4a) *Examine LDX and CBT effects, alone and in combination, for longer-term BED outcomes. Our two-stage design will allow comparison of CBT (i.e., Stage 1 CBT-only short-term) versus the Stage 2 LDX/placebo maintenance treatment (i.e., Stage 2 LDX/placebo following Stage 1 LDX or Stage 1 CBT+LDX) for longer-term outcomes through 18 months.* This will inform clinical questions regarding whether LDX maintenance treatment following either acute LDX treatment or acute combined CBT+LDX differ and whether it offers any additional benefits over acute CBT-only.

(4b) Among *Non-responders* to Stage 1 acute treatments with LDX (i.e., LDX and CBT+LDX), *explore the effectiveness of switching to an alternative medication NB vs placebo* for primary outcomes (reducing binge-eating and reducing weight) and secondary outcomes (binge remission, ED pathology, depression).

(5) Secondary Aims: Generate *cost-effectiveness* estimates of treatments. Incremental cost effectiveness ratios (ICERs) will be computed for LDX vs CBT and LDX+CBT vs CBT (using quality-adjusted life years).

2. **Probable Duration of Project:** State the expected duration of the project, including all follow-up and data analysis activities.

September 1, 2018- August 31, 2025

3. **Background:** Describe the background information that led to the plan for this project. Provide references to support the expectation of obtaining useful scientific data.

**SIGNIFICANCE:** Obesity (OB) is an increasingly prevalent, refractory, and serious public health problem, with estimates that 34% of U.S. adults are obese (Flegal, Carroll et al. 2010). Obesity is considered one of the most serious public health problems of the 21st century. Economic consequences of OB are staggering; associated annual medical costs were estimated at \$147 billion (roughly 10% of all medical spending) (Finkelstein et al. 2009), which reflects continued escalation since estimates of \$75 billion five years earlier (Finkelstein et al.

2004). This study focuses on testing treatments for a high-risk subgroup with binge-eating disorder (BED) (Hudson, Hiripi et al. 2007; Kessler et al., 2013).

Binge Eating Disorder (BED) – An Important Clinical Subgroup of Persons with Obesity

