**Randomization to Stage 1 Treatment.** Eligible participants who provide written informed consent will be randomized in equal proportions to one of three treatments (blocked randomization with random block sizes of 3 and 6 for Stage 1 to obviate any secular trends). Randomization will be stratified by two variables to be tested as moderators (overvaluation of shape/weight (based on  $\geq 4$  EDE item scores) and depression (based on  $> 16$  BDI-II score) ([name], Masheb, Crosby, 2012).

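### Cost-effectiveness: bootstrap intervals are put directly on ICERs with no rule for QALY differences near zero, and CBT+LDX is never compared with LDX

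*Combined protocol and SAP*

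**What the plan says.** The Statement of Purpose, Stage 2 RCT – Secondary Aims, item (5), names two contrasts: "Incremental cost effectiveness ratios (ICERs) will be computed for LDX vs CBT and LDX+CBT vs CBT". Data Analysis, item (5), takes the same comparator for every arm: "the denominator will be the incremental effectiveness of the specific treatment compared to CBT". On uncertainty it has one sentence: "Confidence intervals for the ICERs will be determined using non-parametric bootstrapping".

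QALYs are derived from the SF-12, given before and after treatment and at the follow-ups. On costs: "Repeated assessments will track additional clinician visits and medication use in our RCT as well as outside treatment contacts through the 18-months". The results are to be set beside two earlier economic analyses in BED and to inform later, larger studies.

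The section gives no interval type or confidence level, and no rule for replicates with a zero or negative QALY difference. It mentions no cost-effectiveness plane, net benefit, willingness-to-pay value, dominance rule or acceptability curve. It states no expected QALY difference, QALY SD or cost difference.

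**The concern.** An ICER is a ratio, and its denominator (the QALY difference) can be zero or change sign. A negative ratio can mean that the treatment is cheaper and better (dominant) or dearer and worse (dominated). A positive ratio can mean extra cost for a gain, or a saving for a loss. If the bootstrap replicates lie on both sides of zero QALY difference, sorting their ratios mixes opposite conclusions.

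The plan's own Stage 1 hypotheses make this plausible for both ratios. Data Analysis, item (1), expects no significant difference between CBT and CBT+LDX on binge eating. Between CBT and LDX it expects CBT to do better on binge eating and LDX on weight, so the sign of the QALY difference is hard to predict.

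The second issue is the comparator. The Background (LDX Research Needs) lists, as the first gap for practitioners, whether LDX should be combined with CBT. In economic terms that includes CBT+LDX against LDX, which the cost-effectiveness analysis does not estimate.

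**Working it through.** **Inputs from the documents.** Power Analysis: "with 180 subjects total (60 per treatment group), accounting for up to 20% dropout". This gives 60 × 0.8 = 48 per arm with complete data. Allocation is equal: patients are "randomized in equal proportions to one of three treatments". There is no cost-effectiveness figure to reproduce. As a check on the 48, the plan's Stage 1 detectable effect of d = 0.64 at two-sided alpha 0.025 gives power Φ(0.64·√(48/2) − 2.241) = Φ(0.894) = 0.814 (0.803 with the t distribution). That agrees with the stated figure of more than 80%.

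**Assumed, not in the documents.** QALY SD 0.08 to 0.16, and true QALY differences D of 0.01 and 0.02.

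**Step 1. Wrong sign of the estimate.** SE = SD·√(2/n), and P(wrong sign) = Φ(−D/SE). At n = 48, SE is 0.0163 (SD 0.08) to 0.0327 (SD 0.16).
- D = 0.02: z = 1.22 to 0.61, so 11% to 27%.
- D = 0.01: z = 0.61 to 0.31, so 27% to 38%.

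**Step 2. Average share of replicates with the wrong sign.** Replicates centre on the observed difference, which itself varies around D, so their variance around D is 2·SE². The average share is Φ(−D/(SE·√2)).

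| n per arm | D | Estimate has wrong sign | Mean share of replicates with wrong sign |
|---|---|---|---|
| 48 | 0.02 | 11–27% | 19–33% |
| 48 | 0.01 | 27–38% | 33–41% |
| 60 | 0.02 | 9–25% | 17–31% |
| 60 | 0.01 | 25–37% | 31–40% |

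**Step 3. When is a ratio interval bounded?** A 95% Fieller interval is bounded only if the QALY difference is significant at two-sided 0.05. At n = 48 the probability is 0.08 for a standardized difference of 0.1, 0.165 for 0.2, 0.50 for 0.4 and 0.88 for 0.64. For reference, D = 0.02 in Step 1 is a standardized difference of 0.25 (SD 0.08) to 0.125 (SD 0.16).

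**Step 4. Simulation.** 1,500 trials with 1,000 resamples each and n = 48. Assumptions: QALY SD 0.15, cost difference 1,000, cost SD 1,500, no cost–QALY correlation, willingness to pay 50,000, and percentile intervals for the ICER. A trial straddles zero if more than 2.5% of its replicates fall on each side of zero QALY difference.

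| D | Trials straddling zero | ICER interval coverage | Median ICER interval width | Net benefit coverage |
|---|---|---|---|---|
| 0 | 95% | ratio undefined | 730,000 | 0.95 |
| 0.005 | 95% | 0.78 | 736,000 | 0.94 |
| 0.01 | 93% | 0.91 | 715,000 | 0.94 |
| 0.02 | 89% | 0.95 | 628,000 | 0.94 |
| 0.05 | 63% | 0.96 | 237,000 | 0.94 |
| 0.10 | 9% | 0.96 | 24,000 | 0.94 |

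With 60 per arm the straddling rates are 88% at 0.02, 53% at 0.05 and 5% at 0.10. The net benefit interval is finite in every trial.

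**Step 5. Do the two planned ratios determine CBT+LDX against LDX?** Hold LDX vs CBT at 30,000 per QALY and CBT+LDX vs CBT at 50,000 (illustrative values).

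| LDX minus CBT (cost; QALY) | CBT+LDX minus CBT (cost; QALY) | CBT+LDX minus LDX | Ratio |
|---|---|---|---|
| 300; 0.010 | 2,500; 0.050 | 2,200; 0.040 | 55,000 |
| 600; 0.020 | 3,000; 0.060 | 2,400; 0.040 | 60,000 |
| 600; 0.020 | 1,500; 0.030 | 900; 0.010 | 90,000 |
| 1,200; 0.040 | 1,250; 0.025 | 50; −0.015 | dominated |

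The same two planned ratios are compatible with all four rows, so they do not determine the third.

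**The case against.** The strongest reply is that the plan has not chosen a wrong method. It says bootstrapping without saying percentile intervals, and the same replicates could be plotted on a cost-effectiveness plane and labelled for dominance. That is fair: the text leaves sign changes unaddressed but does not mandate mishandling them. What stands is that the only stated product is an interval on the ratio, and a standard alternative avoids the difficulty.

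A reader might infer that the ICER intervals will be uninterpretable or will have the wrong coverage. The documents do not support that. They give no QALY difference or SD, and under the assumptions above percentile coverage is 0.95–0.96 from a difference of 0.02 upward. From there the problem is reading the limits when replicates straddle zero, not coverage. CBT+LDX is also expected to beat CBT on weight, so its QALY difference need not be near zero.

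The 48 per arm comes from the Stage 1 power statement. Costs and QALYs run to 18 months, further dropout is expected in Stage 2, and follow-up is intended regardless of treatment completion. No sample size is given for this analysis, which is why 48 and 60 are both shown.

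CBT is a reasoned comparator, since the protocol regards it as the best-established treatment. A reader might also infer that the plan will rank the three options misleadingly, but it promises no ranking or decision rule. Leaving out CBT+LDX against LDX invalidates neither planned ICER. Nor are these arms left uncompared throughout: the Stage 1 clinical analyses do compare them. The gap is confined to cost-effectiveness.

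**Conclusion.** The point holds in two parts, as a low-cost improvement to a secondary aim meant to inform later studies.

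First, an interval placed directly on the ICER is hard or impossible to interpret if the QALY difference is small relative to its error. The size of that risk depends on an assumed QALY SD of 0.08–0.16 and on the true difference; the documents supply neither. At about the standardized effect that Stage 1 is powered for (0.64), the interval would usually be usable, but that figure refers to the clinical outcomes and not to QALYs.

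Second, and directly from the text, no cost-effectiveness contrast of CBT+LDX with LDX is planned. If incremental costs and QALYs against CBT were reported alongside the ratios, a reader could subtract to get a point estimate, but not its uncertainty. This is also the contrast on which the plan expects a clinical gain, because it predicts a greater reduction in binge eating with CBT+LDX than with LDX.

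**What to change.** Amend Secondary Aims item (5) and Data Analysis item (5) as follows.

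- Keep the two planned ICERs, so that they can be set beside the two earlier BED analyses.
- Make incremental net monetary benefit (willingness to pay × QALY difference − cost difference) the main uncertainty measure, with bootstrap intervals over a stated range of willingness-to-pay values.
- Plot the bootstrap replicates on the cost-effectiveness plane and give acceptability curves for all three Stage 1 arms.
- Report an ICER interval only when the replicates do not straddle zero QALY difference. Define straddling in advance, for example as more than 2.5% of replicates on each side.
- Add CBT+LDX versus LDX: order the three arms by cost, remove dominated options, and compute incremental ratios along that order from the same replicates of arm mean cost and QALY.

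The cost is a paragraph of plan text and a little more analysis on the same cost and SF-12 data. No extra patients, visits or measures are needed.

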### DATA ANALYSIS

Baseline demographic and clinical characteristics for randomized groups will be compared using chi-square tests for categorical variables, and ANOVA or Kruskal-Wallis tests for continuous variables. Continuous variables will be examined for adherence to normal distribution using normal probability plots and Kolmogorov-Smirnov tests. If normality not satisfied and transformations do not help with achieving normality, alternative analytic strategies will be considered such as generalized estimating equations or nonparametric methods. Dropouts and completers will be compared. Analyses will be intent-to-treat; patients will be followed regardless of treatment completion to minimize missing data. Primary outcomes will be tested at two-sided 0.05 significance level. Secondary analyses will be adjusted for multiple tests using Bonferroni correction.

Overall Data Analysis Strategy will involve MIXED EFFECTS MODELS (Diggle et al, 2002, Gueorguieva & Krystal, 2004) to compare treatments. These models allow for different numbers of observations per subject, use all available data on each subject, and are unaffected by randomly missing data. Further advantage is capacity to test and account for individual-difference contributions to treatment outcomes (Cudeck, 1996; Cudeck & Klebe, 2002; Hedeker et al., 1996; Hedeker & Gibbons, 1996; Singer, 1998). They provide flexibility in modeling the correlation structure of data. In models for each outcome, we will include fixed effects of time, treatment, and interaction between time and treatment, and random subject-level effects. Because we cannot a priori predict the shape of responses over time in each arm of the trial we will first treat time as a categorical predictor and will then test for polynomial trends over time. We will consider different error structures (e.g., AR1, independence) and select the best fitting one based on information criteria. We will

compare dropout patterns between groups and if there are concerns of informative dropout or informative intermittent missing data, we will use pattern mixture models (Hedeker & Gibbons, 1997) to perform sensitivity analyses.

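### Stage 1 is sized on an equal 0.025 split that is valid but less efficient than Holm, and the analysis section does not adopt it, testing primary outcomes at 0.05

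*Combined protocol and SAP*

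**What the plan says.** All of this is in Section I, item 13 (Statistical Considerations) of the combined protocol and SAP.

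- **Power Analysis.** Stage 1 is planned for "at least 80% power at 2-tailed alpha level 0.025 (adjust for 2 outcomes) to detect clinically meaningful effects in Stage 1 for co-primary outcomes". The basis is a trial "with 180 subjects total (60 per treatment group), accounting for up to 20% dropout", and d = 0.64 is called detectable "with more than 80% power at two-sided alpha level of 0.025". The text says this is below the effects expected from earlier data: d = 0.69 to 0.78 "for the comparison of CBT to LDX on binge-eating", and d = 1.53 "for LDX vs CBT on percent weight loss".
- **Data Analysis, opening paragraph.** "Primary outcomes will be tested at two-sided 0.05 significance level". No split or correction is attached to the primaries. The next sentence reads: "Secondary analyses will be adjusted for multiple tests using Bonferroni correction".
- **Data Analysis, item (1), Stage 1.** Four pairwise contrasts carry the primary hypotheses: CBT and CBT+LDX each against LDX on binge eating, and LDX and CBT+LDX each against CBT on weight. No adjustment within an outcome is stated.

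No step-down or hierarchical procedure is mentioned anywhere.

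**The concern.** A fixed equal split gives each outcome 0.025 whatever happens on the other. By the plan's own expectations the two outcomes are very unequal: the weight contrast is all but certain to be significant, while binge eating has the smaller expected effect and is the one at risk. Half of the Stage 1 alpha is therefore tied to a test that does not need it. Holm's step-down procedure rejects everything Bonferroni rejects, controls the same family-wise error over the same tests, needs no assumption about correlation, and releases alpha to the second test once the first is rejected.

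What is at stake depends on which sentence governs the analysis. If it is the 0.025 of the power section, some power on binge eating is given up. If it is the 0.05 of the analysis section, power is not lost, but error over the two outcomes is not controlled at 0.05. The plan does not say which applies.

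**Working it through.** **Inputs.** From the Power Analysis paragraph: 60 per arm, up to 20% dropout, so n = 60 × 0.80 = 48 per arm; alpha 0.025 per outcome; d = 0.64 (detectable), 0.69 to 0.78 (expected, binge eating) and 1.53 (expected, weight).

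**Formula.** Two-sample t test with df = 2n − 2 = 94 and noncentrality d × √(n/2) = d × √24 = 4.899d. Power is the probability that the noncentral t exceeds the two-sided critical value: 2.278 at alpha 0.025 and 1.986 at alpha 0.05.

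**1. The plan's own figure.** For d = 0.64 the noncentrality is 3.135 and power at 0.025 is 80.3%. The effect detectable with 80% power is d = 0.638. Both match the plan.

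**2. Weight.** For d = 1.53 the noncentrality is 7.495, and power at 0.025 exceeds 99.999%.

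**3. Holm over one contrast per outcome.** The smaller p-value is compared with 0.025; if it is rejected, the other is compared with 0.05. With weight all but certain to be rejected, binge eating is in effect tested at 0.05:

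| CBT vs LDX, binge eating | Power at 0.025 | Power at 0.05 (Holm) | Gain, points |
|---|---|---|---|
| d = 0.64 (detectable) | 80.3% | 87.4% | 7.1 |
| d = 0.69 (expected, low) | 86.3% | 91.7% | 5.4 |
| d = 0.78 (expected, high) | 93.7% | 96.6% | 2.9 |

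Equivalently, the effect detectable with 80% power falls from d = 0.638 to d = 0.578. At d = 0.64, matching Holm's 87.4% under the fixed split takes 58 evaluable per arm instead of 48.

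**4. Dependence on the weight effect.** Holm was simulated with 400,000 draws. The correlation between outcomes was set at −0.5, 0 and 0.5; this is an assumption, since the documents give none. With binge eating at d = 0.64:

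- weight at d = 1.53: power 87.3 to 87.4%
- weight at d = 0.64: power 85.0 to 86.9%
- no weight effect: power about 80.5%, almost no gain

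Simulated family-wise error over the two tests was at most 0.050.

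**5. The 0.05 sentence as printed.** Two independent tests, each at 0.05, give 1 − 0.95² = 0.0975.

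**6. All four contrasts.** Holm over four tests uses 0.05/4 = 0.0125, 0.05/3 = 0.0167, 0.05/2 = 0.025 and 0.05 in turn. Its power cannot be computed, because the documents give no expected effect for CBT+LDX versus LDX or CBT+LDX versus CBT. A floor for CBT versus LDX on binge eating is its power at 0.0125: 72.1%, 79.6% and 89.6% at d = 0.64, 0.69 and 0.78.

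**The case against.** The case on the other side is substantial.

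- **The split is not an analysis rule.** The 0.025 appears only in the sample-size text. Read as written, the analysis section already tests binge eating at 0.05, so Holm would add error control and no power. This stands. The power gain is conditional on the 0.025 governing, and the conflict between the two sentences has to be settled first.
- **Binge eating is not left at 80%.** A reader might infer that it is, with Holm worth seven points. That sets weight at its expected effect against binge eating at the smaller detectable effect. At the plan's expected d = 0.69 to 0.78, the 0.025 test already has 86.3 to 93.7% power and Holm adds 5.4 to 2.9 points. This stands.
- **48 per arm is the cautious case.** The mixed models use all available data. With all 60 per arm, an upper bound, power at 0.025 is 89.0%, 93.3% and 97.6% at d = 0.64, 0.69 and 0.78. At 0.05 it is 93.5%, 96.3% and 98.9%, a gain of 4.5, 3.0 and 1.2 points. This stands as a bound.
- **Four contrasts, not two.** A two-test Holm does not control error over all four hypothesised contrasts. This is correct, so the family must be named. The present split has the same gap, so it is no reason to prefer the split.
- **Intervals.** Bonferroni gives simple matching confidence intervals, and Stage 1 item (1) relies on intervals for the contrasts expected to show no difference. This is a real but small cost.
- **Secondary outcomes.** Holm is never less powerful than Bonferroni there either, but the gain cannot be sized because the plan does not define the secondary family.

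None of this removes Holm's advantage over a fixed split on the same tests.

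**Conclusion.** The point holds as an efficiency improvement combined with a rule that needs stating once. If the 0.025 split governs, Holm over one contrast per outcome raises power for CBT versus LDX on binge eating by about 3 to 7 points at an unchanged family-wise 0.05. This assumes 48 evaluable per arm and a weight effect near the expected d = 1.53. The gain is about 3 to 5 points at the plan's expected binge-eating effects and close to zero if weight shows no effect. If the 0.05 sentence governs as printed, there is no power to recover, and family-wise error is 0.0975 for independent tests.

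A reader might infer that the plan's multiplicity control is wrong or that Stage 1 is underpowered. The documents do not support that: the 0.025 split is valid and meets the plan's own 80% target. Nor do they support a claim that a two-test Holm protects all four Stage 1 contrasts.

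**What to change.** 1. In the opening paragraph of Data Analysis, replace the sentence on primary outcomes with one rule: Holm at family-wise two-sided 0.05 across the two Stage 1 co-primary outcomes. Keep the Stage 2 relapse test separately at 0.05, as the power section has it.
2. Name the family. Either take one contrast per outcome, for example CBT versus LDX on binge eating and LDX versus CBT on weight, or apply Holm to all four contrasts in Stage 1 item (1). The second option covers more but starts at 0.0125, so the gains in the table do not carry over to it. Its power would need assumed effects for the two CBT+LDX contrasts.
3. Align the Power Analysis paragraph with that rule. Its 0.025 can stay as the first Holm step for the two-contrast family.
4. Replace Bonferroni with Holm for the secondary outcomes and list the tests in that family.

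The cost is a few sentences, settled before unblinded analysis, with no change to sample size or data collection. Multiplicity-adjusted confidence intervals become less simple; unadjusted intervals can still be reported.
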